12.14.1. Rationale

The purpose of this sub-study is to collect PK samples in a subset of subjects (n=200) randomized to daprodustat in the main study to enable exploratory exposure-response and exposure-safety analyses.

12.14.2. Objectives and Endpoints

Objectives	Endpoints
Primary	

 To summarize the PK parameters of daprodustat and three major metabolites in ND subjects 	
 Plasma daprodustat, M2, M3, and M13 PK parameters pre-dose trough (C_{tau}) and C_{max}
Exploratory	

 Evaluate graphical relationships between exposure parameters and selected efficacy endpoints 	
 Scatter plots of daprodustat PK parameters (C_{tau} and C_{max}) dose normalized to 1 mg vs. percent time in range during EP. Scatter plots of average daprodustat dose during EP vs. percent time in range during EP. Scatter plots of daprodustat PK parameters (C_{tau} and C_{max}) dose normalized to average dose during EP vs. percent time in range during EP. Scatter plots of daprodustat PK parameters (C_{tau} and C_{max}) dose normalized to 1 mg vs. change from baseline of Hgb during EP. Scatter plots of average daprodustat dose during EP vs. change from baseline of Hgb during EP. Scatter plots of daprodustat PK parameters (C_{tau} and C_{max}) dose normalized to average dose during EP vs. change from baseline of Hgb during EP.

 The evaluate graphical relationships between daprodustat exposure and MACE and the combined safety endpoint of MACE + thromboembolic event+ hospitalization for HF 	
 Boxplots of daprodustat PK parameters (C_{tau} and C_{max}) dose normalized to 1 mg by subjects with or without MACE or combined safety endpoint. Boxplots of daprodustat PK parameters (C_{tau} and C_{max}) dose normalized to dose at time of MACE or combined safety endpoint (or end of treatment if no endpoint) by subjects with or without MACE or combined safety endpoint.

12.14.3. Study Design

This is a multicenter sub-study of daprodustat study 200808 (the main study). Approximately 200 subjects from centers in selected countries that are participating in the main study will be invited to participate in the PK sub-study.

12.14.4. Additional Inclusion Criteria

- Signed written informed consent prior to beginning sub-study-related procedures (subject must understand the aims, procedures, and possible consequences of the sub-study). Note: Consent to participate in the sub-study is separate from consent to participate in the main study.
- Subject must be receiving randomized daprodustat treatment in the main study.
- Subjects must not be transitioning or already transitioned to dialysis.

12.14.5. Study Assessments

Blood samples will be collected at any single study visit from the Week 4 through Week 52 visit (i.e., PK is collected at one visit only, based on convenience for the subject/site). Samples will be collected at the following times with respect to dosing of randomized treatment:

- Predose, 0.5h, 1h, 2h and 3h post dose.

On the day of the scheduled PK visit:

- The subject is to be instructed **not** to take their dose at home before the visit, but to take the dose in the clinic after the pre-dose sample is collected.
- The dose taken in the **clinic should be from the same bottle(s) the subject has been using prior to the PK visit**, and **not** from any newly dispensed bottle(s) at the PK visit (Note: a subject placed on a dose hold at the previous visit **should not** have PK samples taken; PK collection should be delayed until the visit after the subject has restarted study treatment).
- Record the date and actual time of the dose taken in the clinic and the three doses prior to the visit, and the date and actual time of all PK samples collected. Samples may be collected within ± 20 min of the planned collected time.

Plasma PK analysis will be performed under the control of GSK PTS-DMPK/Scinovo, the details of which will be included in the SRM. Concentrations of main daprodustat and metabolites (GSK2391220 (M2), GSK2531403 (M3), and GSK2531401 (M13)) will be determined in plasma samples using the currently approved bioanalytical methodology. Raw data will be archived at the bioanalytical site.

12.14.6. Sample Size

It is estimated that 150 sub-study subjects are required to have approximately 80% power that the MACE rate in the sub-study is within 20% of the MACE rate in main study. To account for missing or non-evaluable PK samples, approximately 200 subjects will be enrolled. See Section 9.2.3 for more information about sample size adjustments.

Approximately 30% (n~50) of subjects in this sub-study would be expected to meet the combined safety endpoint (and n~100 subjects would not). Based on a between subject variability (CVb%) estimate for C_{\max} and C_{τ} of up to 100% (as seen in a prior Phase 1 study in CKD and from population PK analysis), 50 subjects would be sufficient to have approximately 80% power that the 95% CI around the geometric mean is within 0.6 to 1.4 times the estimate. This is considered sufficient precision for the descriptive analysis proposed.

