4.2. Type and Number of Subjects

This study will randomize approximately 4500 subjects (2250 subjects per treatment arm) with anemia associated with CKD not on dialysis and will enroll two groups of subjects:

- Group 1 (not using ESAs): subjects not currently receiving ESAs with a baseline HemoCue Hgb 8-10 g/dL.
- Group 2 (ESA users): subjects currently receiving ESA with a baseline HemoCue Hgb 8-11 g/dL.

The proportion of subjects not using ESAs (Group 1) and ESA-users (Group 2) randomized into the study is expected to be approximately 60% and 40%, respectively.

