9.2. Sample Size Considerations

9.2.1. Sample Size Assumptions

The size of this event driven trial is based on the co-primary CV safety objective and is determined by a fixed event target of 664 adjudicated first MACE. This provides approximately 90% power to establish non-inferiority assuming a true underlying 3% lower relative risk of MACE in favor of daprodustat compared to darbepoetin (i.e., hazard ratio=0.97) and 82% power for non-inferiority under the assumption that the true underlying risk of MACE is the same in both arms (i.e., hazard ratio=1). Other assumptions behind the sample size calculation include:

- Projected annual adjudicated first MACE rate of 9.3%. All-cause death is expected to be the most prevalent component, followed by non-fatal MI and then non-fatal stroke (projected break down of 50%, 30% and 20% respectively).
- Variance under the alternative hypothesis (i.e. hazard ratio=0.97)
- 1% annual lost to follow-up without vital status
- A two-sided 95% CI is used for analysis

The target of 664 adjudicated first MACE will permit a two-sided 95% CI of (0.859, 1.164) to describe the results for an observed hazard ratio of 1. The largest hazard ratio point estimate (two-sided 95% CI) that would meet the statistical criterion for non-inferiority is 1.074 (0.922, 1.250) and for superiority, the minimum observable effect would be a 14.1% relative risk reduction in favor of daprodustat, corresponding to a hazard ratio of 0.859.

Conditional on both co-primary endpoints achieving non-inferiority at the one-sided 2.5% level, statistical testing will progress to evaluate MACE and the principal secondary endpoints for superiority. These tests will be multiplicity adjusted, details are provided in Section 9.4.3.

Based on expected enrolment and an annual MACE rate of 9.3%, it is anticipated that the the 664 adjudicated first MACE target will be reached approximately 4.2 years from when the first subject is randomized. It is anticipated that more than 80% of randomized subjects will have the opportunity for a minimum of 1 year exposure to treatment and thus the opportunity to complete the EP (Weeks 28 to 52). Exposure to daprodustat is expected to be in the region of 4000 patient years with median patient follow-up expected to exceed 2 years.

Note: The country-specific requirements for France ONLY for the sample size consideration are provided in [Appendix 15](#) (see Section 12.15.1, Item 2 for details).

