9.2.3. Sample Size Re-estimation or Adjustment

GSK and the Executive Steering Committee will review blinded data periodically during the course of the study and should emerging data suggest that the overall event rate and/or the enrollment rate (main study or sub-studies) diverges significantly from protocol assumptions either the sample size required to achieve the event target and/or the requirement for a minimum of one year follow-up may be adjusted.

The current COVID-19 pandemic has significantly impacted subject enrolment such that it is considered likely that enrolment will be closed prior to reaching the target of 4,500 subjects.

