The co-primary endpoints will each be tested using a **one-sided 2.5%** significance level and **the relevant confidence bound of the a-two-sided 95% CI (upper bound for MACE and lower bound for the Hgb co-primary endpoint)**. The type I error rate will be strictly controlled at the **one-sided 2.5%** level across the co-primary analyses as both non-inferiority tests need to be met for the trial to be considered successful and for statistical analysis to proceed to evaluate MACE superiority and superiority for the principal secondary objectives/endpoints.

Section 9.1.1. CV Safety (MACE) Co-Primary Hypothesis; last paragraph. Added two-sided to 95% CIs.

Statistical significance of non-inferiority will be assessed at the ~~two~~**one-sided 2.5%** level. A Cox-Proportional-Hazards-Regression model, adjusting for treatment and prognostic randomization stratification factors (region and current ESA use), will be used to estimate the hazard-ratio, its **two-sided 95% CI** and to generate the p-value for the non-inferiority test. Non-inferiority will be achieved if the upper limit of the two-sided 95% CI is below the margin of 1.20.

Section 9.1.2. Hgb efficacy Co-Primary Hypothesis; 3rd paragraph. Changed to one-sided 2.5% level and added two-sided to 95% CI.

Statistical significance of non-inferiority will be assessed at the ~~two~~**one-sided 2.5%** level. An ANCOVA model including prognostic randomization stratification factors (dialysis type and region), baseline Hgb and treatment will be used to obtain a point estimate and the **two-sided 95% CI** for the treatment difference (daprodustat -rhEPO) and generate the p-value for the non-inferiority test

Section 9.2.1. Sample Size Assumptions; paragraph after bullets. Changed to one-sided 2.5% level and added two-sided to 95% CI.

The target of 945 adjudicated first MACE will permit a **two-sided 95% CI** of (0.880, 1.136) to describe the results for an observed hazard ratio of 1. The largest hazard ratio point estimate (**two-sided 95% CI**) that would meet the statistical criterion for non-inferiority is 1.056 (0.930, 1.200) and for superiority, the minimum observable effect would be a 12% relative risk reduction in favor of daprodustat, corresponding to a hazard ratio of 0.880.

Conditional on both co-primary endpoints achieving non-inferiority at the **one-sided 2.5%** level, statistical testing will progress to evaluate MACE and the principal secondary endpoints for superiority.

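### The PK sub-study's stated power of about 80% comes to about 70% on the protocol's current target of 664 MACE in 4500 subjects

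*Protocol*

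**What the plan says.** Appendix 14, Section 12.14.6, gives the reason for the number of evaluable subjects: "It is estimated that 150 sub-study subjects are required to have approximately 80% power that the MACE rate in the sub-study is within 20" per cent of the MACE rate in the main study. The margin above 150 has a separate purpose: "To account for missing or non-evaluable PK samples, approximately 200 subjects will be enrolled".

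The main-study inputs on which that probability depends are stated elsewhere in the protocol:

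- Section 9.2.1: the trial size is "determined by a fixed event target of 664 adjudicated first MACE".
- Section 4.2: "This study will randomize approximately 4500 subjects (2250 subjects per treatment arm").
- Section 9.2.1: "Projected annual adjudicated first MACE rate of 9.3" per cent, and "Exposure to daprodustat is expected to be in the region of 4000 patient years with median patient follow-up expected to exceed 2 years".
- Section 9.2.3: because of the pandemic, "it is considered likely that enrolment will be closed prior to reaching the target of 4,500 subjects". No expected final number is given.

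Section 12.14.6 does not say which MACE proportion, follow-up time or formula lies behind its 80%.

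**The concern.** With the sample size and the tolerance fixed, the probability that a sample proportion falls within 20% of the true one depends only on that proportion. The rarer the event, the less precise the relative estimate. Amendment 5 cut the event target from 945 to 664 and left the planned number of subjects at about 4500, so the expected proportion with MACE fell. The list of changes for Amendment 5 carries the new target through the synopsis and Sections 4.1, 6.3.5 and 9.2, but shows no edit to Section 12.14.6.

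This probability is the reason the protocol gives for needing 150 evaluable subjects. If it is too high, the protocol overstates how closely the PK sample can be expected to match the main trial's MACE rate. The exposure-by-MACE boxplots in Section 12.14.2 would then rest on fewer MACE subjects than the planning figure implies.

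**Working it through.** **Reading adopted.** The statement is taken as a two-sided relative tolerance on a proportion. With p the main-study MACE proportion and n = 150:

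P = 2Φ(0.2p / √(p(1−p)/n)) − 1

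**Does any set of inputs give 80%?** The Amendment 3 change log in Appendix 16 quotes the superseded planning text: "The target of 945 adjudicated first MACE will permit a" stated confidence interval. With that target:

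- p = 945/4500 = 0.210
- standard error = √(0.21 × 0.79/150) = 0.03326
- 0.042/0.03326 = 1.263, so P = 79.3% (exact binomial 77.2%)
- n needed for 80% = (1.2816/0.2)² × 0.79/0.21, about 155

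This agrees with 150 subjects and approximately 80%.

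**Current inputs.**

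- p = 664/4500 = 0.1476
- standard error = √(0.1476 × 0.8524/150) = 0.02896
- 0.02951/0.02896 = 1.019, so P = 69.2%
- Exact binomial: the expected count is 22.1 and the tolerance covers 18 to 26 events, so P = 70.1%
- n needed for 80% = 41.06 × 0.8524/0.1476, about 238

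**From the exposure projection.** 4000 patient-years × 0.093 = 372 events, and 372/2250 = 0.165, which gives 72.4%. This treats treatment exposure as follow-up time. Doubled over two arms it implies 744 events, so it is somewhat generous against a target of 664.

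**If enrolment closes early.** The final N values below are assumptions; the protocol names none.

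| Main-study N | p = 664/N | P, normal approximation | P, exact | n for 80% |
|---|---|---|---|---|
| 4500 (stated) | 0.148 | 69.2% | 70.1% | 238 |
| 4000 (assumed) | 0.166 | 72.5% | 72.8% | 207 |
| 3700 (assumed) | 0.179 | 74.8% | 75.8% | 188 |

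**When does 80% return?** For P = 80% with n = 150, p/(1−p) = (1.2816/0.2)²/150 = 0.274, so p = 0.215 and N = 664/0.215, about 3090. To come within two points (78%), p = 0.2005 and N is about 3310.

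**Does the enrolment margin cover it?** With all 200 enrolled subjects evaluable, P at 664/4500 is 76.1%.

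**The case against.** The strongest reply is that the protocol states no method and probably will not reach 4500, so the 69% may be too harsh. Both parts have force.

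- **Size of the trial.** 664 events at 9.3% per year need about 664/0.093 = 7140 patient-years. Over 4500 subjects that is about 1.6 years each, which sits poorly with a median follow-up above 2 years. An average of 2 years would imply about 3570 subjects, p = 18.6% and P of about 76%. This moves the figure towards the upper end of the range but does not reach 80%.
- **Method.** A continuity correction gives 74.3% at 664/4500 and 78.9% at an assumed 3700, close to what the protocol claims. The same correction gives 82.7% for 945/4500, so a gap between the two targets remains under either method.
- **Population.** The sub-study takes only subjects on daprodustat who have not moved and are not moving to dialysis, sampled between Weeks 4 and 52. The whole-trial proportion is therefore a proxy. The protocol gives no other.

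A reader might go further in three ways that the documents do not support.

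- **That the 80% must be left over from 945 events.** Any p near 0.20-0.21 reproduces it. For example, 9.3% per year over a uniform 2.5 years gives 79.0%, although that implies about 930 events in 4500 subjects. The change log is also weak evidence of what this protocol's Section 12.14.6 said under the 945-event target, because its PK sample-size entry is headed as concerning dialysis subjects. The old target is a probable explanation and no more.
- **That the expected 30% (about 50 subjects) with the combined safety endpoint is stale and should be scaled down.** Multiplying 45 of 150 by the ratio of MACE proportions would give about 32 to 38. The endpoint also includes heart-failure hospitalization and thromboembolic events, for which the protocol gives no rates, so nothing supports proportional scaling.
- **That the sub-study must be enlarged to about 238 evaluable subjects.** No test or decision depends on the figure.

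**Conclusion.** The stated power is not delivered on the protocol's own current inputs. At 664 events in 4500 subjects, 150 evaluable subjects give about 69-70%, roughly 10 points below the stated figure. From the exposure projection it is about 72%. Over an assumed final N of 3700-4500 it is about 70-75%. On the normal approximation it comes near 80% only if about 3300 or fewer subjects are randomized.

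The conclusion rests on reading the statement as a two-sided relative tolerance on a proportion and on using the whole-trial MACE proportion for the sub-study. The practical effect is small: the outputs are descriptive plots and summaries, and neither the main analysis nor any formal comparison uses the figure.

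**What to change.** In Section 12.14.6, restate the probability as about 70% for 150 evaluable subjects at 664 first MACE in 4500 subjects, or about 70-75% over an assumed final N of 3700-4500. Show the formula and the assumed MACE proportion beside it, so that the figure can be updated once enrolment closes. Leave enrolment at about 200. Do not rescale the combined-endpoint figure from the MACE ratio.

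The cost is one sentence in Appendix 14 and a less favourable number. Nothing changes in conduct, recruitment or the main analysis.

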12.14.7. PK/Pharmacodynamic Analyses

The 'PK Population' is defined as subjects for whom a PK sample was obtained and analyzed. This will be the population used for all the PK displays.

The following plasma PK parameters will be determined for daprodustat and metabolites: C_{τ} (pre-dose) and C_{\max} .

Plasma daprodustat and metabolites concentration data will be listed and summarized by planned collection time and daprodustat dose administered at PK visit. PK parameter data will be listed and summarized by daprodustat dose administered at PK visit, and dose-normalized (per mg) PK parameter data will be summarized.

All PK data will be stored in the Archives, GlaxoSmithKline Pharmaceuticals, R&D.

Based on exploratory graphs (Section 12.14.2), and the efficacy and safety results from the main study, post-hoc exploratory exposure-response/safety modelling may be conducted, including exploratory graphics with metabolites. In the event that sub-study recruitment does not make its pre-specified target, a limited number of analyses and data summaries may be produced depending on the number of subjects with data. Further details will be provided in the RAP of the main study.

12.15. Appendix 15: Country Specific Requirements

12.15.1. French Administrative Considerations and Specifics Requirements

This appendix includes all the requirements of the French law (n°2004-806 of 9th August 2004), and identifies, item per item, the mandatory modifications or additional information to the study protocol and includes specific GSK requirements.

1. Concerning the « STUDY POPULATION»

In line with the local regulatory requirements, the following text in section «**OTHER STUDY ELIGIBILITY CRITERIA CONSIDERATIONS** » is added: A subject will be eligible for inclusion in this study if he /she is either affiliated to or beneficiary of a social security category.

It is the investigator's responsibility to ensure and to document (in source document - patient notes) that the patient is either affiliated to or beneficiary of a social security category.

2. Concerning the “DATA ANALYSIS AND STATISTICAL CONSIDERATIONS” and specially in the “SAMPLE SIZE ASSUMPTION”

The expected number of patients to be recruited in France is declared to the French regulatory authority.

3. Concerning the “STUDY CONDUCT CONSIDERATIONS”

In section “Regulatory and Ethical Considerations, Including the Informed Consent Process”

Concerning **the process for informing the patient** or his/her legally authorized representative, the following text is added:

French Patient Informed Consent form is a document which summarizes the main features of the study and allows collection of the patient's written consent in duplicate. It also contains a reference to the authorization of L'Agence nationale de sécurité du médicament et des produits de santé (ANSM) and the approval from the French Ethics committee.

Concerning the management of the Patient Informed Consent forms, the following text is added:

The first copy of the Patient Informed Consent form is kept by the investigator. The second is given to the patient or his/her legally authorized representative

- In section concerning the “**NOTIFICATION TO THE HOSPITAL DIRECTOR**” the following text is added:

In accordance with Article L1123-13 of the Public Health Code, the Hospital Director is informed of the commitment to the trial in his establishment. The Hospital Director is supplied with the protocol and any information needed for the

financial disposition, the name of the investigator(s), the number of sites involved in his establishment and the estimated time schedule of the trial (R.1123-63).

- In section concerning the “**INFORMATION TO THE HOSPITAL PHARMACIST**” the following text is added:

In accordance with Article R.1123-64 of the Public Health Code, the Hospital Pharmacist is informed of the commitment to the trial in his establishment. The Pharmacist is supplied with a copy of the protocol (which allows him to dispense the drug(s) of the trial according to the trial methodology), all information concerning the product(s) of the trial (e.g. included in the CIB), the name of the investigator(s), the number of sites involved in his establishment and the estimated time schedule of the trial.

- In section “**DATA MANAGEMENT**” the following text is added:

Within the framework of this clinical trial, data regarding the identity of the investigators and/or co-investigators and/or the pharmacist if applicable, involved in this clinical trial, and data regarding the patients recruited in this clinical trial (patient number, treatment number, patient status with respect to the clinical trial, dates of visit, medical data) will be collected and computerized in GSK data bases by GlaxoSmithKline Laboratory or on its behalf, for reasons of follow up, clinical trial management and using the results of said clinical trial. According to the Act n° 78-17 of 6th January 1978 further modified, each of these people aforesaid has a right of access, correction and opposition on their own data through GlaxoSmithKline Laboratory (Clinical Operations Department).

4. **Monitoring visits**

The Health Institution and the Investigator agree to receive on a regular basis a Clinical Research Assistant (CRA) of GLAXOSMITHKLINE or of a service provider designated by GLAXOSMITHKLINE. The Health Institution and the Investigator agree to be available for any phone call and to systematically answer to all correspondence regarding the Study from GLAXOSMITHKLINE or from a service provider designated by GLAXOSMITHKLINE. In addition, the Health Institution and the Investigator agree that the CRA or the service provider designated by GLAXOSMITHKLINE have direct access to all the data concerning the Study (test results, medical record, etc.). This consultation of the information by GLAXOSMITHKLINE is required to validate the data registered in the eCRF, in particular by comparing them directly to the source data. In accordance with the legal and regulatory requirements, the strictest confidentiality will be respected.

5. **Data entry into the eCRF**

The Health Institution and the Investigator agree to meet deadlines, terms and conditions of the Study's eCRF use here below:

The Health Institution and the Investigator undertake:

- 1) That the Investigator and the staff of the investigator center make themselves available to attend the training concerning the computer system dedicated to the eCRF of the Study provided by GLAXOSMITHKLINE or by a company designated by GLAXOSMITHKLINE.

- 2) That the Investigator and the staff of the investigator center use the IT Equipment loaned and/or the access codes only for the purpose of which they are intended and for which they have been entrusted to them, namely for the Study achievement, to the exclusion of any other use.
- 3) That the Investigator and the staff of the investigator center use the IT Equipment loaned according to the specifications and manufacturer's recommendations which will have been provided by GLAXOSMITHKLINE.
- 4) To keep the IT Equipment and/or access codes in a safe and secure place and to only authorize the use of this IT Equipment by investigator center staff designated by the principal investigator to enter the data of the Study.
- 5) That the Investigator and the staff of the investigator center enter the data of the eCRF related to a patient visit in the 3 days following the date of the patient visit or, for the patient test results, in the 3 days following the reception of the results of such tests.
- 6) That the Investigator resolves and returns to GLAXOSMITHKLINE the data queries issued by GLAXOSMITHKLINE or a service provider designated by GLAXOSMITHKLINE within 7 days after the reception of the request of clarification or in a period of one (1) day during the final stage of clarification of the data base or in such other period as provided by GLAXOSMITHKLINE and/or a company designated by GLAXOSMITHKLINE.
- 7) To be responsible for the installation and payment of the required Internet connections needed for the use of the IT Equipment, Computer systems and/or access codes.
- 8) To return at the end of the Study the IT Equipment and/or access codes to GLAXOSMITHKLINE or to any company designated by GLAXOSMITHKLINE and any training material and documentation. The IT Equipment cannot under any circumstances be kept by the Health Institution or the Investigator for any reason whatsoever.

6. CTR publication

It is expressly specified that GLAXOSMITHKLINE and/or the Sponsor can make available to the public the results of the Study by the posting of the said results on a website of the GLAXOSMITHKLINE GROUP named Clinical Trial Register (CTR) including the registration of all the clinical trials conduct by the GLAXOSMITHKLINE Group and this before or after the publication of such results by any other process.

7. Data Protection French Law of 6 January 1978 (CNIL)

In accordance with the Data Protection French Law of 6 January 1978 as modified, computer files used by GLAXOSMITHKLINE to monitor and follow the implementation and the progress of the Study are declared with the CNIL by GLAXOSMITHKLINE. The Investigator has regarding the processing data related to him a right of access, of rectification and of opposition with GLAXOSMITHKLINE in accordance with the legal provisions. This information can be transferred or be accessed to other entities of GLAXOSMITHKLINE Group in France, Britain or United States, what the Investigator agrees by the signature of the present Protocol.

